6.2 Patient-reported Outcomes

Pain-related outcomes of interest include:

- Pain interference from baseline to three months, measured using an eight-item survey of the NIH Patient Reported Outcomes Measurement Information System (PROMIS).²⁹ Items assess the extent that pain interferes with physical, cognitive, emotional, and recreational activities.
- Social isolation, collected using another NIH PROMIS measure, with an eight-item scale on lacking companionship, feeling left out, and feeling isolated.³⁰
- We will also assess intervention effects on pain intensity, physical functioning, depression, and anxiety using NIH PROMIS measures.³¹⁻³⁴
- Additional aspects of health-related quality of life associated with chronic pain will be collected using NIH PROMIS measures for sleep, social functioning, global physical, mental, and social well-being.
- Participant ratings of global improvement. A single item, 7 point rating on the Patient Global Impression of Change scale will assess minimal clinically important difference in changes in participants' pain.³⁵
- Pain beliefs and attitudes will be assessed with scales for pain catastrophizing³⁶ and pain self-efficacy.^{37,38}
- Social Support in Chronic Pain, a 6-item measure of perceived support related to pain.³⁹
- Internalized Stigma of Chronic Pain (ISCP) scale, 21 items with five subscales on enacted and internalized chronic pain stigma: alienation, stereotype endorsement, discrimination experience, social withdrawal, and stigma resistance (Cronbach's $\alpha = 0.724$).⁴¹ Prior research has documented an association between this measure and pain-related cognitive functioning, such as pain self-efficacy and pain catastrophizing.⁴¹
- Intersectional Discrimination Index measures anticipated, day-to-day, and major discrimination that do not focus on a single axis of discrimination (e.g., racism, homophobia) to capture intersectional categories.⁴²
- Descriptive covariates collected at baseline will include: socio-demographic variables (age,

sex, race/ethnicity, place of birth, level of education, household income, marital status, employment status, and health insurance status) and a substance use screener (using HEAL CDE). Clinical data including chronic pain diagnosis, concomitant conditions, medications, and treatments received for pain will be obtained from participants' medical record.

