7.3 Adverse Events and Serious Adverse Events

An **adverse event (AE)** is defined as any unfavorable and unintended diagnosis, symptom, sign (including an abnormal laboratory finding), syndrome or disease which either occurs during the study, having been absent at baseline, or if present at baseline, appears to worsen. Adverse events will be recorded regardless of their relationship to the study intervention.

A **serious adverse event (SAE)** is defined as any untoward medical occurrence that results in one or more of the following outcomes:

- Death
- A life-threatening event
- Inpatient hospitalization or prolongation of existing hospitalization
- A persistent or significant disability/incapacity
- A congenital anomaly or birth defect
- An important medical event based upon appropriate medical judgment

Information on minor adverse events will be collected as solicited events. These will be listed in alphabetical order on an electronic case report form. Study staff will collect this information at participants' weekly visits. Using an electronic data collection system, such as RedCap or Qualtrics, helps to assure that the reporting and data collection systems avoid double capture. Describe which AEs will be collected as solicited events. The adverse event form will also have items to capture any unsolicited events such as serious adverse events; these will be documented by study staff without direct input from participants. Adverse events will be reported on a monthly basis to the data and safety independent monitor. Serious adverse events will be reported immediately.

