7.6 Safety Monitoring

The Principal Investigator (PI) will be responsible for ensuring participants' safety on a daily basis. The full study team will monitor participant symptoms, performance status, and review questionnaires and clinical test results. Participants will be provided with a 24-hour contact number to report any persistent problems or emergencies. If any concerns arise, they will immediately be brought to the attention of study PI, [name], who will consult with her mentors as needed. The PI will be responsible for reporting any adverse events and conducting the annual safety review of study data. Study data will be reviewed for adverse events, subject complaints, deviations from the protocol design, any unexpected incidents associated with the study procedures, and explanations for any subject withdrawals from the study.

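### Section 7.3 gives serious and other unsolicited adverse events no active, scheduled source, and its wording on participant input conflicts with Sections 7.5 and 7.6

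*Combined protocol and SAP*

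**What the plan says.** Section 7.3 of the combined protocol and SAP divides the capture of adverse events in two.

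- Minor events: "Information on minor adverse events will be collected as solicited events", and "Study staff will collect this information at participants' weekly visits".
- Other events have their own items on the same form, with serious adverse events as the named example. Of them the section says that "these will be documented by study staff without direct input from participants".

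The same section lists "Inpatient hospitalization or prolongation of existing hospitalization" among the outcomes that make an event serious, and sets a broad scope: "Adverse events will be recorded regardless of their relationship to the study intervention".

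Other sections bear on the point. The opening of Section 7 has staff complete event reports every week for all participants, without saying where the information comes from. Section 7.5 provides for following up any event that a participant reports. Section 7.6 states: "Participants will be provided with a 24-hour contact number to report any persistent problems or emergencies". It sends concerns to the principal investigator, who must report adverse events. On records, Section 5 plans an extraction of health record data to describe usual care, and Section 6.2 adds: "Clinical data including chronic pain diagnosis, concomitant conditions, medications, and treatments received for pain will be obtained from participants' medical record".

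**The concern.** A hospital stay, an emergency visit or a fall at home will usually happen away from study sessions, and the participant is often the first person who could tell the study about it. Read literally, Section 7.3 has staff ask about minor reactions and then keeps the participant out of the documentation of exactly those larger events. It puts no other source in the participant's place.

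Two things are at stake. First, Section 7.3 requires serious events to go to the independent monitor at once, and that cannot happen for an event of which staff never learn. Second, Section 7.1 already expects no serious events. A count of zero would then be hard to interpret: it could mean that none occurred, or that none were looked for. If the chance of detection also depends on the arm, a comparison of event counts between arms would mix the effect of the interventions with the effect of being seen every week.

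**Working it through.** The plan gives no figure to reproduce here. The check was to read each safety and data-source section for a step that would actively find a serious event that staff did not witness.

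| Section | What it provides | Active, scheduled search for serious events? |
|---|---|---|
| 4.4 | Survey and interview three months after baseline on symptoms, quality of life and pain care | None described |
| 5 and 6.2 | Health record data, to describe usual care and clinical background | Not stated as a purpose |
| 7, opening | Weekly event reporting for all participants | Source of information not stated |
| 7.2 | Its heading promises methods and timing; the text gives published rates for acupuncture | No |
| 7.3 | Weekly solicitation of minor events; form items for unsolicited ones | No; participant input is excluded if read literally |
| 7.4 | Staff training and reporting deadlines | No; it covers events already known |
| 7.5 | Follow-up of events that participants report | No; it starts after a report |
| 7.6 | 24-hour number; review of questionnaires and study data | No; the number works only if the participant calls |

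**Two readings of the clause in 7.3.** (a) Literal: participants do not contribute to the record of serious events. This contradicts 7.5 and 7.6, which rely on their reports, and it fits poorly with recording every event regardless of cause. (b) Administrative: staff rather than participants fill in those form items. This removes the contradiction, but the table does not change. No section asks about admissions, emergency visits or injuries. The gap in active ascertainment therefore remains under either reading.

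**Difference between arms.** Section 3 gives four arms of 10, 40 in total.

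- Arms with weekly sessions: 3 × 10 = 30 participants (30/40 = 75%).
- Waitlist arm with no weekly session described: 10 participants (10/40 = 25%).
- Weekly visits at which the 7.3 form could be completed over 12 weeks: up to 12 for a participant in one intervention, and none described for the waitlist.
- Attendance also matters. The adherence goal in Section 6.1 is a mean of six sessions. A participant in one intervention who attends six would be seen in 6 of 12 weeks (50%), assuming that a form is completed only at attended sessions.
- The follow-up question in 7.5 is tied to acupuncture visits, which 10 + 10 = 20 of the 40 participants are assigned to have.

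So the stated contact points differ by arm and by attendance, while the opening of Section 7 promises weekly reporting for everyone.

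**The case against.** The strongest case on the other side is that Section 7.3 is merely badly worded and that the rest of Section 7 covers the matter. Participants have an emergency number, concerns go straight to the investigator, any event they report is followed, staff are trained to report all events, and reporting is weekly for everyone. Unsolicited events are by definition not prompted by a checklist, and the clause can mean only that staff complete the items. A leftover template instruction in the same paragraph, telling the author to describe the solicited events, points to unfinished drafting rather than a deliberate choice.

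Much of this stands, and it rules out several stronger inferences that a reader might draw.

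- That unwitnessed events have no route into the safety data. They do, through 7.5, 7.6 and the weekly reports. The routes are passive or unspecified, and none is linked to the items for serious events on the form.
- That Section 6.2 confines the record extraction to the items it names. The list is introduced as non-exhaustive. The documents support only that no search for serious events is stated.
- That every reporting deadline would fail. The 10-working-day report to the IRB in 7.4 covers a narrow class: on-site serious events and unexpected events that are related to the research and change the risk/benefit or require protocol and consent changes. An unrelated admission elsewhere would not ordinarily trigger it even if known.
- That the small share of time spent with staff measures the loss. Sessions take 12 × 2 h = 24 h (group visits), 12 × 0.5 to 0.75 h = 6 to 9 h (acupuncture) or 30 to 33 h (both), out of 12 × 7 × 24 = 2,016 h, which is 0.3% to 1.6%. That describes an outpatient trial. It does not count missed events, because participants can report afterwards.
- That the larger trial would inherit a false safety statement. That is speculation.

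What the objection does not supply is a scheduled question or check for serious events, or an explanation of how the waitlist arm is covered.

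**Conclusion.** The point holds in a limited form. Section 7.3 names no active, scheduled source for serious and other unsolicited events. Its clause on participant input, taken at face value, conflicts with 7.5, 7.6 and its own rule on scope. Ascertainment of unwitnessed events then depends on participants volunteering them or on weekly reports of unstated origin.

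The weakness in active ascertainment concerns all 40 participants. The possible difference between arms concerns the 10 on the waitlist against the other 30. The number of events missed cannot be estimated, because the documents give neither an expected rate of admissions in this population nor a detection probability.

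The conclusion assumes that no manual or form outside these documents already contains such a question, and that the waitlist arm has no weekly contact. Section 8 mentions follow-up phone calls, but for checking discontinuation criteria and without a schedule. The primary feasibility outcome, the percentage of confirmed eligible patients randomized, is not affected.

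**What to change.** 1. In Section 7.3, delete the clause that excludes participants' direct input, or state that staff complete and classify these items using what participants report. Remove the leftover template instruction.
2. Reconcile 7.3 with the opening of Section 7, 7.5 and 7.6, so that one passage states the source and timing of information on serious events.
3. Add one open question to the existing adverse event form and the three-month survey: any new or worse health problem, emergency visit, hospital stay or injury since the last contact. Staff still judge seriousness and relatedness.
4. Ask it on the same schedule in all four arms, by a short phone or text contact where there is no weekly visit. The same contact can serve for missed sessions. Without this step, the added question would widen the difference between arms.
5. Enter admissions and emergency visits found in the planned health record review on the same form, over the same period in every arm. Report that source separately, so that readers can see what came from asking and what came from the record.

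The cost is protocol wording, one question, a field in an extraction already planned, and brief regular contacts with 10 waitlist participants. More unrelated events will be recorded, and the waitlist arm will have slightly more study contact than the present text describes.

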7.4 Reporting Procedures

As part of training and orientation for the study, all research staff will be alerted to the importance and necessity of reporting of all adverse events that occur during the study. Forms for adverse event reporting will include sections to document relatedness and severity. Any adverse events will be immediately reported to the PI ([name]), dealt with immediately, and if necessary, discussed with mentors and advisors. If it is determined that a participant is experiencing a high level of distress, the activity will be stopped. Any small or large adverse events will also be discussed during weekly research meetings. Registered nurses and medical doctors will be available at the SFGH Clinical Research Center (CRC) to supervise and assist with procedures. Acute, adverse reactions to acupuncture or any other procedure will be treated by a physician. Reporting of adverse events will follow requirements mandated by the Committee on Human Research, with concurrent reporting to the Research Services Analyst (RSA) at the CRC. In addition, the RSA will receive a verbal or e-mail report of any serious adverse event (graded 3 or higher) that occurs during the conduct of the study within 48 hours. On-site SAEs and unexpected AEs of any grade that are both related to research and result in a change to risk/benefit or

require protocol and consent modifications will be reported to the UCSF IRB within 10 working days of PI awareness. All other AEs related to the research that are both non-serious (grades 1-2) and expected will be reported annually.

7.5 Follow-up for Adverse Events

Any adverse event reported by participants will be followed until resolved or considered stable. At subsequent acupuncture treatment visits, study staff will ask participants about the status of the reported adverse event at least once or until the participant reports that the adverse event has resolved.

7.6 Safety Monitoring

The Principal Investigator (PI) will be responsible for ensuring participants' safety on a daily basis. The full study team will monitor participant symptoms, performance status, and review questionnaires and clinical test results. Participants will be provided with a 24-hour contact number to report any persistent problems or emergencies. If any concerns arise, they will immediately be brought to the attention of study PI, [name], who will consult with her mentors as needed. The PI will be responsible for reporting any adverse events and conducting the annual safety review of study data. Study data will be reviewed for adverse events, subject complaints, deviations from the protocol design, any unexpected incidents associated with the study procedures, and explanations for any subject withdrawals from the study.

8. INTERVENTION DISCONTINUATION

A subject may be discontinued from study treatment at any time if the subject, the investigator, or the Sponsor feels that it is not in the subject's best interest to continue. The following is a list of possible reasons for study treatment discontinuation:

- Subject withdrawal of consent
- Subject is not compliant with study procedures such as repeatedly not completing data collection
- Adverse event that in the opinion of the investigator would be in the best interest of the subject to discontinue study treatment
- Protocol violation requiring discontinuation of study treatment
- Lost to follow-up
- Sponsor request for early termination of study

Trained study staff will regularly assess whether participants meet criteria for discontinuation at acupuncture treatment visits, data collection visits, and follow-up phone calls.

All subjects are free to withdraw from participation at any time, for any reason, specified or unspecified, and without prejudice. If a subject is withdrawn from treatment due to an adverse event, the subject will be followed and treated by the Investigator until the abnormal parameter or symptom has resolved or stabilized.

All subjects who discontinue study treatment should come in for an early discontinuation visit as soon as possible and then should be encouraged to complete all remaining scheduled visits and procedures.

Reasonable attempts will be made by the investigator to provide a reason for subject withdrawals. The reason for the subject's withdrawal from the study will be specified in the subject's source documents. Refer to Section 10 for early termination procedures. Subjects who withdraw after Week 8 but prior to Week 12 should be encouraged to come in for a final visit (and the procedures to be followed would include those for their next scheduled visit).

Subjects who withdraw from the study will not be replaced.

9. STATISTICAL CONSIDERATIONS

9.1 Sample Size Rationale

The study will enroll 40 participants. As a small pilot study designed to pilot the refined intervention, we did not conduct a formal power calculation but instead used a confidence interval approach to determine sample size, based on current recommendations for small samples. Findings from the pilot study are intended to help plan for a future trial by estimating key parameters. However, small trials often overestimate treatment effects and the convention of basing power calculations on pilot trials has received considerable scrutiny (Kraemer, 2006). Our approach will be to determine whether the effect size from the pilot is clinically meaningful (i.e., within an 80% confidence interval of a pre-determined effect size) and justifies proceeding with future research. To determine this, Cocks and Torgenson (2013) recommend that a pilot sample size should be at least 9% of the sample size of the planned main study.

Based on data of minimally important differences for PROMIS pain measures, our main study would aim to detect a standardized effect size of 0.25. Using our pilot data to estimate within group correlation and a sample size calculator designed for individually randomized group trials, we estimated a sample size of 360. Using Cocks and Torgenson's method, the corresponding pilot sample size should be at least 32. Using an estimated attrition of 20%, we aim to enroll 40 participants. With 20 participants randomized to each of the study interventions, we will have sufficient power to determine if the effect size estimated from the pilot is within the range of clinical significance using a one-sided 80% confidence interval. If the estimated effect is zero or less, the upper 80% CI will not contain our target effect size of 0.25, and we would not proceed with a main study. If the estimated effect size from the pilot is larger than zero, and the study procedures are feasible and acceptable, then we would have sufficient preliminary data to proceed with the main study.

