9.2 Statistical Analysis Plan

Descriptive analyses

Baseline characteristics of participants, including sociodemographics and health condition variables, will be summarized to determine sample generalizability, and compared to assess group equivalency. We will look at summary statistics for data cleaning (e.g., means, ranges)

and then consider distributions by randomized arm as a check of balanced distribution across groups.

Analysis of Feasibility. Feasibility outcomes will be analyzed by computing percentages, with 95% confidence intervals, of rates of retention and enrollment. We will also conduct a thematic analysis of qualitative responses on participants' experiences with the study and acceptability of group acupuncture.

Assessment of implementation, defined as quality and consistency of the intervention delivery across staff, will be focused on evaluating core components and content of IGMV and parameters in STRICTA guidelines for group acupuncture. IGMV facilitators will complete a short survey after each session documenting content and time spent on each component. Acupuncturists will complete charting for each treatment provided.

Analysis of Patient-Reported Outcome Measures. This study is powered to assess exploratory effects and pilot feasibility, not for confirmatory analysis. Nonetheless, we will analyze clinical outcomes in a manner similar to that planned for the main study to make a preliminary assessment of the strength of the effects; to identify any unexpected issues with missing data, skewed distributions, or outliers; and to refine the statistical analysis plan. Relative (mean \pm SD) measures of effect sizes will be calculated as change from baseline to post-intervention for all outcome variables. Planned analyses include: within group changes from baseline to Week 12, group acupuncture vs. no acupuncture, and IGMV vs. no IGMV.

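### Section 9.1 presents a futility screen as having power to judge clinical significance; a null intervention meets its effect criterion half the time

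*Combined protocol and SAP*

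**What the plan says.** Section 9.1 says that, for a pilot of this size, "we did not conduct a formal power calculation", and that a confidence-interval approach was used in its place. The reasoning starts from the later trial: "our main study would aim to detect a standardized effect size of 0.25", for which "we estimated a sample size of 360". A published rule that "a pilot sample size should be at least 9% of the sample size of the planned main study" then gives 32, raised to 40 for 20% attrition.

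The section treats the pilot effect as clinically meaningful if it is compatible with the pre-set effect size at the 80% level. It claims that with 20 per intervention "we will have sufficient power to determine if the effect size estimated from the pilot is within the range of clinical significance". The interval named for this judgement is one-sided at the 80% level. The decision rule follows. An estimate of zero or less means no main study. The go condition is worded: "If the estimated effect size from the pilot is larger than zero, and the study procedures are feasible and acceptable". When both parts hold, the preliminary data are taken as sufficient to proceed.

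Section 9.2 adds: "This study is powered to assess exploratory effects and pilot feasibility, not for confirmatory analysis". It plans two between-group comparisons: acupuncture against no acupuncture, and integrative group medical visits (IGMV) against none. Section 9.1 does not say whether one or both must give an estimate above zero.

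**The concern.** An upper confidence limit that reaches a target shows that the data are compatible with the target. It does not show that the effect is of that size, or that there is any effect. Under the rule as written, an estimate of 0.02 SD passes the effect criterion, and Section 9.1 describes passing as a finding about clinical significance.

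The claim of sufficient power comes without a figure. Section 9.1 gives no probability of passing under no effect or under the target effect. Section 9.2 says the study is powered for exploratory effects, also without a figure. A reader deciding whether to support a 360-patient trial cannot tell how much a pass is worth and, on the present wording, is likely to give it too much weight.

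**Working it through.** **Inputs from Section 9.1.** Target effect 0.25 SD; main-trial size 360; pilot fraction 9%; attrition 20%; 40 enrolled; one-sided 80% interval (z = 0.8416). Section 3 gives four equal arms of 10, so each comparison is 20 against 20 randomised, or about 16 against 16 after attrition.

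**Assumed, because the documents do not state them.** Main trial at two-sided 5% with 80% power; a symmetric, unbiased effect estimate; outcome SD of 1; no separate allowance for clustering.

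**1. The plan's own figure.** 0.09 × 360 = 32.4, stated as 32. Then 32 / 0.80 = 40. The enrolment figure reproduces.

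**2. Where the 9% comes from.** (0.8416 / (1.9600 + 0.8416))² = 0.0902. Under the assumed main-trial error rates, the rule picks the pilot size at which an estimate of zero has its one-sided 80% upper limit at the target. A true effect equal to the target then gives an estimate above zero 80% of the time. The rule limits the chance of stopping an intervention that works to about 20%. Nothing in it limits the chance of passing one that does not.

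**3. Standard error.** For one comparison in a balanced 2×2 design with n analysed and residual variance v, SE = 2√(v/n). I take v = 1 (no gain from baseline adjustment) and the value at which 360 gives 80% power for 0.25: v = 360 × (0.25/2.8016)² / 4 = 0.717.

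**4. Pass rate of the effect criterion.** P(estimate > 0) = Φ(d/SE), where d is the true effect.

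| n | v | SE | d = 0 | d = 0.25 | Upper limit at estimate 0 |
|---|---|---|---|---|---|
| 32 | 1 | 0.354 | 0.50 | 0.760 | 0.298 |
| 32 | 0.717 | 0.299 | 0.50 | 0.798 | 0.252 |
| 40 | 1 | 0.316 | 0.50 | 0.785 | 0.266 |
| 40 | 0.717 | 0.268 | 0.50 | 0.825 | 0.225 |

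The 0.50 column is Φ(0) and does not depend on n, v or clustering. A pass is 0.760/0.50 = 1.52 to 0.825/0.50 = 1.65 times as likely at the target as at no effect.

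**5. Reading the criterion as the interval itself.** If passing means that the upper limit reaches 0.25, the null pass rate is 55% or 50% at n = 32 (v = 1, then about 0.72) and 52% or 46% at n = 40. The conclusion does not depend on which reading is taken.

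**6. Two interventions, both null, independent estimates.** At least one passes: 1 − 0.5² = 0.75. Both pass: 0.5² = 0.25. In 20,000 simulated balanced 2×2 trials per setting, the two estimates had correlation near zero and at least one was positive in 74.7–74.9% of runs.

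**7. The feasibility condition.** If the procedures prove feasible and acceptable with probability q, independently of the effect estimate, the null rates are multiplied by q. With q = 0.8 (an illustration), 50% becomes 40%, 75% becomes 60% and 25% becomes 20%.

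**The case against.** The strongest defence is that this is a sensible pilot screen. A true effect of 0.25 passes about 76–82% of the time, which is what the 9% rule is built to deliver, and a team might fairly call that sufficient power. Section 9.1 warns that small trials tend to overestimate effects, and Section 9.2 disclaims confirmatory analysis. A permissive screen is legitimate at this stage. All of that stands. It supports describing the criterion as a screen; it does not support saying that the screen determines clinical significance.

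Four stronger readings are tempting, and the documents do not bear them out.

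- A reader might infer that the go rule passes a useless intervention half the time. The rule also requires feasible and acceptable procedures, so 50% is the rate for the effect criterion alone and an upper bound for a go. Feasibility carries no information about efficacy, however, so it does not rescue the claim.
- A reader might take 75% as the false-pass rate for the pair. It applies only if either intervention suffices; if both must pass it is 25%. Section 9.1 does not say which.
- A reader might say that an estimate above zero means exactly that 0.25 has not been ruled out. At n = 40 and v = 0.717, an estimate of 0.02 has an upper limit of 0.02 + 0.225 = 0.245, which does exclude 0.25.
- A reader might see a flat contradiction between having done no power calculation and having sufficient power. The section says that a confidence-interval approach replaced the power calculation, so this is better read as loose use of the word power with no figure behind it.

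**Conclusion.** The point holds as one about what a pass can support. The claim of sufficient power to judge clinical significance is wrong as written. The effect criterion is met with probability 50% by a null intervention and about 76–82% by one with the target effect. The shortcoming is the undisclosed null pass rate and the language built on it; sensitivity to the target is not the problem.

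The 50% needs only a symmetric, unbiased estimate. The 76–82% rests on 32 to 40 analysed, residual variance between 1.0 and about 0.72, the assumed main-trial error rates and no separate clustering allowance; a larger variance would lower it. The 75% and 25% also need the two estimates to be independent, which is reasonable in a balanced 2×2 design. No participant is affected. What is at risk is over-reading a positive pilot in the case for the 360-patient trial, and the wording should be corrected.

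**What to change.** In Section 9.1, delete the clause claiming "we will have sufficient power to determine if the effect size estimated from the pilot is within the range of clinical significance" and the description of a compatible estimate as clinically meaningful. Replace them with text along these lines:

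> The effect criterion (estimate above zero) is a futility screen. Meeting it is not evidence of a clinically meaningful effect. An intervention with no effect meets it with probability 50%; one with a true effect of 0.25 SD meets it with probability about 76–82%, assuming 32 to 40 analysed and residual variance of 1.0 to about 0.72. [One / Both] of the two interventions must meet it; if neither has an effect, this happens with probability [75% / 25%], assuming independent estimates. A decision to proceed also requires feasible and acceptable procedures, so these null rates are upper bounds for that decision.

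The sponsor has to choose between one and both, and the matching null rate follows.

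In Section 9.2, replace the statement that the study is powered for exploratory effects and feasibility with one saying that it is not powered for effects and that effect estimates are exploratory.

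The one-sided 80% bound and the feasibility condition can stay as they are. Replacing the effect criterion with the feasibility goals in Section 6.1, or moving to a two-sided interval, would change the decision rule and is not needed to correct this point.

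Cost: wording in two sections. No participants or data are added; the stated figures become less favourable.
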